### **2.5.2.4 SINS score at 3 and 6 months**

Mean, SD, median, min, max of the SINS score changes at 3 months and 6 months after radiation treatment will be summarized. Wilcoxin rank sum test will be used to compare the difference between treatment arms in changes at 3 month and 6 month respectively (Table 21).

The analysis will be repeated for each of the 6 categories in SINS, i.e., by Location, Pain, Bone Lesion, Radiographic Spinal Alignment, Vertebral Body Collapse, and Posterolateral Involvement.(Table 21b).

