1.2 Secondary Objectives

To assess both treatment arms with respect to:

- Complete pain response in the treatment area at 6 months post-radiation, based on the International Bone Metastases Consensus Working Party Criteria.
- Radiation site progression-free survival (RSS PFS) at 3 and 6 months, using MRI imaging.
- Spinal instability as measured by the Spinal Instability Neoplastic Score at 3 and 6 months.
- Overall survival.
- Adverse event profile, using the Common Terminology Criteria for Adverse Events version 4.0 (CTCAE v 4.0).
- Health-Related Quality of Life as measured by the EORTC QLQ-C30 and QLQ-BM22 instruments.
- Economic analysis as measured by the EuroQol EQ-5D-5L instrument.
- Radiotherapy Quality Assurance (RTQA) compliance, using prospectively-defined protocol-specified quality assurance measures.

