5.1 Eligibility Criteria

There will be NO EXCEPTIONS to eligibility requirements at the time of randomization. Questions about eligibility criteria should be addressed prior to calling for randomization.

The eligibility criteria for this study have been carefully considered. Eligibility criteria are standards used to ensure that patients who enter this study are medically appropriate candidates for this therapy. For the safety of the patients, as well as to ensure that the results of this study can be useful for making treatment decisions regarding other patients with similar diseases, it is important that no exceptions be made to these criteria for admission to the study.

Patients must fulfill all of the following criteria to be eligible for admission to the study:

- 5.1.1 Histologic or cytologic diagnosis of cancer (excluding seminoma, small cell lung cancer and hematologic primaries).
- 5.1.2 Spinal metastasis documented with MRI and suitable for treatment with radiotherapy with the following characteristics:
 - Painful, as defined by a pain score ≥ 2 for worst pain in the planned target treatment volume;
 - ≤ 3 consecutive spinal segments involved by tumour to be included in the planned target volume. The patient may have other spinal metastases to be treated as per the radiation oncologist's discretion, but the eligible spinal metastatic site for SC.24 has to be one where there is pain and no more than 3 consecutive segments to be included as clinical target volume and appropriate for either 20 Gy in 5 fractions or 24 Gy in 2 fractions per the randomization.
- 5.1.3 There is no plan to change the pain medication on the first day of protocol treatment with radiotherapy.
- 5.1.4 ECOG Performance Status 0-2.
- 5.1.5 Seen by a radiation oncologist and judged to be appropriate for participation in this study including ability to tolerate protocol radiotherapy (SBRT or CRT).
- 5.1.6 Age of 18 years or older.
- 5.1.7 Patient is able and willing to complete the Patient Diary (pain and analgesic use).

AMEND #1: 2017-FEB-02; AMEND #2: 2018-APR-03

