5.2 Ineligibility Criteria

Patients who fulfill any of the following criteria are not eligible for admission to the study:

- 5.2.1 Patients who have a pacemaker, such that MRI cannot be performed or treatment cannot be delivered safely.
- 5.2.2 Patients with prior treatment with any radionuclide within 30 days prior to randomization.
- 5.2.3 Patients with prior radiation to the spinal segment intended to be treated with protocol radiotherapy such that the protocol therapy cannot be delivered as intended.
- 5.2.4 Patients with prior surgery to the spinal segment intended to be treated with protocol radiotherapy.

AMEND #2: 2018-APR-03

- 5.2.5 Patients who have received chemotherapy within 1 week prior to administration of protocol radiotherapy or who are expected/planned to receive chemotherapy within one week of completing protocol radiotherapy. Centre guidelines regarding administration of targeted non-cytotoxic therapy must be followed with the proviso that no systemic anticancer therapy should be administered within 24 hours prior to and post-radiotherapy. Endocrine therapy may be administered during radiotherapy as per the discretion of the treating physician.
- 5.2.6 Patients with spine instability as judged by a *Spinal Instability Neoplastic Score (SINS)* [Fisher 2010] of more than 12 (see Appendix III).
- 5.2.7 Patients with symptomatic spinal cord compression or cauda equina syndrome resulting from bony compression or epidural compression of the spinal cord and cauda equina, respectively. Symptomatic refers to neurologic deficit in the form of motor, bowel or bladder dysfunction
- 5.2.8 Pregnant or lactating women.

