14.3 Sample Size and Duration of Study

For the randomized phase II portion of the study, a convenience sample size of 54 patients is considered sufficient to evaluate whether accrual is feasible. This sample size would also provide an opportunity to estimate the CRT and SBRT 3 month complete pain relief response rates, which would provide the basis for the sample size calculation of the future randomized controlled trial. We chose a sample size that provides for standard error rates in both treatment arms to be less than 10%. Assuming that the CRT response rate is 10% to 30%, with 27 patients, the standard error for the estimated response rate will be 5.8% to 8.8%, respectively. Assuming that the SBRT response rate is about 30% to 50%, with 27 patients, the standard error for the estimated response rate would be 8.8% to 9.8%, respectively.

The trial was activated in July 2015. By November 2016, 44 patients had been enrolled onto the study and the accrual rate indicated that the sample size would be reached in 18 months, thereby meeting the primary objective of the phase II feasibility study. Other metrics of trial conduct were examined including treatment related toxicity and tolerability as well compliance with radiotherapy including quality assurance measures. No safety signals were detected in either arm. Notably, spinal fracture within the treatment fields occurred in 2 patients - both on the conventional treatment arm (CRT). Compliance with protocol mandated radiotherapy and quality assurance measures was high.

Based on the demonstration of feasibility of trial conduct and continued need to critically evaluate the efficacy of SBRT in the treatment of painful spinal metastases, approval was sought and granted in January 2017 for conversion of the study design from a randomized phase II feasibility study to a randomized phase II/III study comparing the two radiotherapy treatment strategies.

Sample size estimate for the phase III controlled trial is with a two-sided 5% level test and 80% power. Based on the results of a randomized phase II trial [*Sprave 2018*] with similar enrollment and radiobiology criteria as the current study, we estimate the complete pain responses will be 20% for the CRT and 40% for the SBRT treatment arms, respectively.

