14.6 Secondary Endpoint and Analysis

Complete pain response in the treatment area at 6 months post-radiation. All analyses for the primary endpoint will be performed for the complete pain response at 6 months post-radiation.

AMEND #1: 2017-FEB-02; AMEND #2: 2018-APR-03; AMEND #3: 2018-OCT-31

Radiation site progression-free survival (RSS PFS) is defined as the time from the date of randomization to the date of documented local progression, as defined in Section 10.2.2; or the date of death. Patients who have not progressed or died by the cutoff date of final analysis, RSS PFS will be censored on the date of the last disease assessment. A Kaplan-Meier curve for proportions of RSS PFS in each treatment arm will be displayed. The RSS PFS rates at 3 and 6 months and their 95% confidence intervals will be estimated. The 95% confidence intervals for the medial RSS PFS will be computed using the method of Brookmeyer and Crowley. The difference in distributions of RSS PFS in the two treatment arms will be compared using the log-rank test stratified by the stratification factors at randomization except study centre. Other potential important factors that predict RSS PFS will be assessed using Cox regression. Overall survival will be analysed similarly.

The incidence of acute severe adverse incidences for each arm will be calculated with its 95% confidence interval, and the analyses will be performed in a tiered comparison, i.e., comparing the overall incidence rates between treatment arms first, then comparison of radiotherapy and disease related symptoms and compared by means of Chi-square analysis or Fisher exact test.

SINS scores will be summarized for data at baseline, 3 and 6 months evaluations. The potential prognostic effects of baseline SINS score on the complete pain response at 3 months post-radiation and the overall survival will be explored using logistic and Cox regression models respectively.

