APPENDIX III - SPINAL INSTABILITY NEOPLASTIC SCORE (SINS) SCORESHEET

| | |
|--|---------------------|
| 
Location
 
 • 3 points: Junctional (C0-C2, C7-T2, T11-L1, L5-S1) • 2 points: Mobile Spine (C3-C6, L2-L4) • 1 point: Semi-rigid (T3-T10) • 0 points: Rigid (S2-S5) | 
Score: _____
 |
| 
Pain relief with recumbency and/or pain with movement/loading of the spine
 
 • 3 points: Yes • 1 point: No (occasional pain but not mechanical) • 0 points: Pain free lesion | 
Score: _____
 |
| 
Bone lesion
 
 • 2 points: Lytic • 1 point: Mixed (lytic/blastic) • 0 points: Blastic | 
Score: _____
 |
| 
Radiographic spinal alignment
 
 • 4 points: Subluxation / translation present • 2 points: De novo deformiye (kyphosis / scoliosis) • 0 points: Normal alignment | 
Score: _____
 |
| 
Vertebral body collapse
 
 • 3 points: > 50% collapse • 2 points: < 50% collapse • 1 point: No collapse with > 50% body involved • 0 points: None of the above | 
Score: _____
 |
| 
Posterolateral involvement of the spinal elements (facet, pedicle or costovertebral joint fracture or replacement with tumour)
 
 • 3 points: Bilateral • 1 point: Unilateral • 0 points: None of the above | 
Score: _____
 |
| 
Sum Score: _____
 | |
| 
Adapted from Fisher 2010. Interpretation:
 
 • Sum Score 0 – 6: Stable • Sum Score 7 - 12: Indeterminate (possibly impending) instability • Sum Score 13 – 18: Instability | |

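### The SINS comparison plans no arm difference with a confidence interval and no adjustment, although baseline SINS, histology and mass are all collected

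*SAP*

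**What the plan says.** Protocol 1.2 states the objective as "Spinal instability as measured by the Spinal Instability Neoplastic Score at 3 and 6 months". The SAP's analysis, in 2.5.2.4, is "Mean, SD, median, min, max of the SINS score changes at 3 months and 6 months after radiation treatment will be summarized", followed by a Wilcoxon rank-sum comparison of the arms at each time. The Table 21 shell has rows for median, minimum, maximum, mean and SD of change, and a p-value column. Table 21b repeats this for the six component items. Neither has a place for a difference between arms or its confidence interval.

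SAP 2.3 lists histology and mass as the factors that adjust analyses where appropriate. They are used for complete pain response, radiation site progression-free survival and overall survival (SAP 2.5.2), but not for SINS. Baseline SINS is tabulated in Table 7, with the classes 0-6, 7-12 and 13-18, and is a covariate in the logistic model for complete pain response (SAP 2.5.2.1).

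Protocol 14.6 adds: "SINS scores will be summarized for data at baseline, 3 and 6 months evaluations". That refers to the scores, not only to their change. It names no statistics, and the SAP has no table shell for scores at follow-up.

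**The concern.** A Wilcoxon p-value says whether the two distributions of change differ detectably. It does not say by how many SINS points, or how precisely that is known. Vertebral compression fracture is named as the second most serious SBRT risk (protocol 3.1.2.1), so a reader will want the size of the difference and the range of differences that the data exclude. A non-significant p-value alone cannot give this.

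A reader could work out an unadjusted difference in mean change, with an interval, from the means, SDs and numbers in Table 21. The adjusted difference cannot be recovered from the planned tables. The covariates are already in the database, so leaving it out saves nothing.

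**Working it through.** **Inputs.** The documents give no design figure for SINS: no expected difference, SD, baseline-to-follow-up correlation or evaluable rate. The trial's 228 patients at 1:1 allocation set a ceiling of 114 per arm. Only relative precision can be examined, over assumed values.

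**Precision of the two differences.** Let rho be the within-arm correlation of baseline and follow-up SINS, and k the baseline SD divided by the follow-up SD. In units of the follow-up variance, per patient:

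- variance of change = 1 + k² - 2·rho·k
- residual variance after linear adjustment for baseline = 1 - rho²
- the first minus the second = (k - rho)², which is never negative.

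So in large samples the adjusted difference is at least as precise as the unadjusted difference in change, and equally precise only when rho = k. Any further gain from histology and mass is not quantified here.

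Ratio of adjusted to change-score variance, R = (1 - rho²)/(1 + k² - 2·rho·k), with the ratio of interval widths (√R) in brackets:

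| k | rho 0.5 | rho 0.7 | rho 0.8 | rho 0.93 |
|---|---|---|---|---|
| 1.0 | 0.75 (0.87) | 0.85 (0.92) | 0.90 (0.95) | 0.965 (0.98) |
| 0.9 | 0.82 (0.91) | 0.93 (0.96) | 0.97 (0.99) | 0.99 (1.00) |
| 0.8 | 0.89 (0.94) | 0.98 (0.99) | 1.00 (1.00) | 0.89 (0.94) |

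Example: k = 1, rho = 0.5 gives 0.75/(2 - 1) = 0.75 and √0.75 = 0.87. With k = 0.8 and rho = 0.8 the ratio is 0.36/0.36 = 1, so there is no gain.

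The same grid as power, for a test of the change score assumed to have 80%, is Φ(2.8016/√R - 1.96): 90/86/84/81% for k = 1.0, 87/83/81/80% for k = 0.9 and 84/81/80/84% for k = 0.8. These figures compare two normal-theory estimates. They do not evaluate the planned Wilcoxon test.

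**Where this trial may lie.** The SINS location item does not change for a fixed target segment, which pushes rho up. Patients with SINS above 12 are ineligible (protocol 5.2.6), which may hold the baseline SD below the follow-up SD. Both suggest that the gain could be small.

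**The optional class summary.** Change statistics do not fix the number of patients who reach 13 or more. Suppose 23 of 114 patients gain 2 points and 91 do not change: median 0, mean 46/114 = 0.40, SD 0.81, minimum 0, maximum 2. If the gains start from 11-12, 23 patients (20%) are newly at 13 or more; if they start from 4-6, none are. Such a count would be imprecise. For an assumed 10% versus 5%, Fisher power is 9% at 60 per arm and 22% at 114. The 95% intervals are -5.2 to 15.7 points (6/60 vs 3/60) and -2.7 to 11.8 points (11/114 vs 6/114).

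The count can also differ by arm for reasons other than structure. Eligibility requires "Painful, as defined by a pain score ≥ 2 for worst pain in the planned target treatment volume", and the SINS pain item gives "0 points: Pain free lesion". For planning, protocol 14.3 says "we estimate the complete pain responses will be 20% for the CRT and 40% for the SBRT treatment arms, respectively". Assume a true structural rate of 10% in both arms, response independent of structure, and every complete responder falling below 13. The count then reads 0.10 × 0.80 = 8% for CRT and 0.10 × 0.60 = 6% for SBRT. That 2-point gap is not a maximum, because the item can also fall from 3 to 1 without complete response. If a further 20% (CRT) and 40% (SBRT) drop below 13 in that way, the reading is 0.10 × 0.60 = 6% against 0.10 × 0.20 = 2%, a gap of 4 points.

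**The case against.** The Wilcoxon test is a sound choice for a bounded integer score. Adjustment is promised only where appropriate, and the quality-of-life change scores are also compared without it. If most changes are zero, a mean difference from a linear model is not clearly the better summary. The gain rests on assumed values and can be nil. All of this stands. It is why the planned test stays and the adjusted difference is offered as an estimate beside it. It does not remove the case for an effect estimate with an interval.

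A reader might infer something stronger: that the plan conceals how many patients become unstable, since Appendix III labels a total as "Sum Score 13 – 18: Instability" and the SAP uses the classes only at baseline. The documents do not support that. The objective is instability as measured by the score; the classes are interpretation bands and an entry cut-off, and no document makes crossing 12 an endpoint. Protocol 14.6 already commits to summarising the follow-up scores. Structural harm is reported through the vertebral collapse item in Table 21b and the fractures and compressions in Table 32b. A follow-up class table would be useful description, but its absence is not an error.

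**Conclusion.** The point holds as a low-cost improvement to a secondary analysis. The planned SINS comparison is valid, but it includes no arm difference with a confidence interval and does not use baseline SINS or the two stratification factors. The adjusted difference has, in large samples, at least the precision of the unadjusted difference in change. Over the assumed grid its interval is 0 to 13% narrower. That rests on a linear relation, similar within-arm variances and correlations in the two arms, and values of rho and k that the documents do not give. It would be wrong to infer that the Wilcoxon test is invalid or that the linear model would have more power than it.

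The estimate, like the planned test, describes patients with a SINS assessment at that time and does not deal with deaths or missed assessments. The primary endpoint, sample size and alpha are untouched.

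**What to change.** Keep the change summaries and the Wilcoxon test in SAP 2.5.2.4. Add to Table 21, at 3 and at 6 months, the SBRT minus CRT difference in follow-up SINS with its 95% CI, from a linear model adjusted for baseline SINS, histology and mass. Use the same patients as the planned comparison, and label the result as estimation alongside the Wilcoxon p-value. The cost is a sentence of SAP text and one row per time; no new data are needed.

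Optional: meet protocol 14.6 by adding the follow-up scores to Table 21, with the classes 0-6, 7-12 and 13-18 by arm, as description only. Note beside it that the pain item can lower the 13-or-more count more in the arm with better pain relief, and that it should be read with Tables 21b and 32b. If a count with the pain item held at its baseline value is also shown, state that it is not the standard SINS and that it also removes genuine new mechanical pain (item rising from 1 to 3).

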### **2.5.2.5 Overall survival**

K-M estimate of OS distribution will be displayed by treatment arm, and log-rank test stratified by stratification factors of Histology (radioresistant vs. radiosensitive) and “Mass” on imaging (present vs. absent) will be used to test the difference and Cox regression model stratified by the stratification factors will be used to estimate the HR and its 95% C.I. (table 22). For patients who died, their causes of death will be presented in table 23.

The 3 months and 6 months OS rate will be estimated from the K-M curves by treatment arm.

**Subgroup analysis:** OS will be performed based on patients’ stratification factors at baseline, i. e. Histology (radioresistant vs. radiosensitive) and “Mass”\* on imaging (present vs. absent) (Table 24) with interaction p-value to tell if any differential treatment effect across levels of stratification factors.

## **2.6 RT Exposure**

### **2.6.0 Time from randomization to start of RT**

Mean, STD, median, min, max of the time from randomization to the date of starting RT in days, summarized by treatment arm (table 25a)

### **2.6.1 Treatment duration and dose**

Mean, median, min, max of SBRT/CRT duration in days, and total RT dose received will be summarized by treatment arm. (table 25, 26)

### **2.6.2 Treatment compliance**

Treatment compliance will be defined as the ability to plan and deliver the protocol specified radiotherapy according to prospectively defined criteria relating to dose and fractionation schedule.

Treatment compliance will be monitored on an ongoing basis by Central Office and the designated radiotherapy quality assurance reviewer and will be described for both arms.

A table will summarize whether radiation was given according to protocol specified dose and time schedules; present the number and percentage with minor, major deviation from RASIN. (Based on centre reported and central reviewed respectively). Table 27 and 28.

### **2.6.3 Concomitant Medications (followup)**

Number and percent of patients with concomitant medication will be summarized by treatment arm. (Table 29).

### **2.6.3 Cancer Treatment (followup)**

Number and percent of patients received cancer treatment will be summarized by treatment arm. (table 30)

## **2.7: Safety**

### **2.7.1: Definitions and variables**

All toxicity/side effects data collected post randomization will be included in the analyses of toxicities.

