6.0 PRE-TREATMENT EVALUATION
 (See Appendix I)

| Investigations | | Timing |
|--|--|--|
| History and Physical Exam including: | 
 Physical Examination ECOG PS | Within 4 weeks prior to randomization |
| Radiology | 
 MRI entire spine | Within 8 weeks prior to randomization |
| Pain / Analgesic Assessment | 
 Patient Diary* | Within 7 days prior to randomization ALSO: Repeat at Day 0** |
| Adverse Events** | Baseline adverse event evaluation (to document residual adverse event from previous therapy and baseline symptoms): events ≥ grade 2 only | Within 7 days prior to randomization |
| Health-Related Quality of Life*** | 
 EORTC QLQ-C30 and QLQ-BM22 questionnaires | Within 7 days prior to randomization ALSO: Repeat at Day 0** |
| Economic Analysis*** | 
 EQ-5D-5L questionnaire | Within 7 days prior to randomization ALSO: Repeat at Day 0** |
| Other Assessments | 
 SINS score (use scoring sheet♦) | Within 7 days prior to randomization |
| | 
 Pregnancy test (for women of child bearing potential only) | Within 7 days prior to randomization |
| Correlative Studies♦♦♦ | 
 Optional, for consenting patients only: Plasma and Serum | After randomization and prior to start of treatment |

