#### 2.4.1.7 Baseline Adverse Events (table 8)

Baseline adverse event were collected within 7 days prior to randomization, and summarized according to NCI CTCAE V4.0.

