#### **2.7.1.1: Adverse events during follow up**

Adverse Events Related to RT reported at Follow-up Contact and experienced during follow-up will be summarized. (table 31). Of special interest, the number of patients who reported the vertebral fractures and spinal cord compression will be summarized by treatment arm (table 31b).

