**Table 31: Adverse Events/Intercurrent Illness (Worst Ever Grade on study)**

Data set: All Treated Patients (SBRT Arm)						
	Number of patients (%)					Any grade
	N=***					
	Worst grade					
	NR	1	2	3	4	
Patients with any AE	** (**)	** (**)	** (**)	** (**)	** (**)	** (**)
Patients with AE within category						
Category 1 	**(**)	**(**)	**(**)	**(**)	**(**)	**(**)
Event 1	**(**)	**(**)	**(**)	**(**)	**(**)	**(**)
Event 2	**(**)	**(**)	**(**)	**(**)	**(**)	**(**)
Event 3	**(**)	**(**)	**(**)	**(**)	**(**)	**(**)
...						
Category 2 	**(**)	**(**)	**(**)	**(**)	**(**)	**(**)
Event 1	**(**)	**(**)	**(**)	**(**)	**(**)	**(**)
...						

(1) Patients may have more than one event within a category.

**NOTE:** In CRT Arm, the same type of table will be made.

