**Table 32. Serious Adverse Events**

Data set: All Treated Patients (SBRT Arm)						
	Number of patients (%) N=***					Any grade
	NR	Worst grade				
		1	2	3	4	
Patients with serious AE within category						
Category 1 	**(**)	**(**)	**(**)	**(**)	**(**)	**(**)
Event 1	**(**)	**(**)	**(**)	**(**)	**(**)	**(**)
...	**(**)	**(**)	**(**)	**(**)	**(**)	**(**)
Category 2 	**(**)	**(**)	**(**)	**(**)	**(**)	**(**)
Event 1	**(**)	**(**)	**(**)	**(**)	**(**)	**(**)
...	**(**)	**(**)	**(**)	**(**)	**(**)	**(**)
Patients with fatal AE within category						
Category 1 	**(**)	**(**)	**(**)	**(**)	**(**)	**(**)
Event 1	**(**)	**(**)	**(**)	**(**)	**(**)	**(**)
...	**(**)	**(**)	**(**)	**(**)	**(**)	**(**)
Category 2 	**(**)	**(**)	**(**)	**(**)	**(**)	**(**)
Event 1	**(**)	**(**)	**(**)	**(**)	**(**)	**(**)
...	**(**)	**(**)	**(**)	**(**)	**(**)	**(**)
Patients with AE leading to hospitalization within category						
Category 1 	**(**)	**(**)	**(**)	**(**)	**(**)	**(**)
Event 1	**(**)	**(**)	**(**)	**(**)	**(**)	**(**)
...	**(**)	**(**)	**(**)	**(**)	**(**)	**(**)
Category 2 	**(**)	**(**)	**(**)	**(**)	**(**)	**(**)
Event 1	**(**)	**(**)	**(**)	**(**)	**(**)	**(**)
...	**(**)	**(**)	**(**)	**(**)	**(**)	**(**)

(1) Patients may have more than one event within a category.

**NOTE:** In CRT Arm, the same type of table will be made.

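### SAP Table 31 reports worst on-study grade without each patient's baseline grade, so symptoms present before radiotherapy can be counted as on-study adverse events

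*SAP*

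**What the plan says.** **Baseline.** Protocol 6.0 requires, within 7 days before randomization and for grade 2 or higher only, a "Baseline adverse event evaluation (to document residual adverse event from previous therapy and baseline symptoms". SAP 2.4.1.7 repeats this: "Baseline adverse event were collected within 7 days prior to randomization, and summarized according to NCI CTCAE V4.0". The results go to Table 8, by arm.

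**On study.** Three places in the SAP describe the content of Table 31, and they differ:

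- SAP 2.7.1: "All toxicity/side effects data collected post randomization will be included in the analyses of toxicities".
- SAP 2.7.1.1: "Adverse Events Related to RT reported at Follow-up Contact and experienced during follow-up will be summarized. (table 31").
- The shell: "Table 31: Adverse Events/Intercurrent Illness (Worst Ever Grade on study"), for treated patients, one table per arm, with no attribution column and no baseline column.

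**Start of counting.** SAP 2.7.1 counts from randomization. Protocol 10.1.4 makes patients evaluable for adverse events from their first treatment. Protocol 8.0 allows up to 3 weeks between the two.

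**Comparison.** Protocol 14.6 plans a tiered chi-square or Fisher comparison of acute severe events: overall incidence first, then radiotherapy- and disease-related symptoms. SAP 2.7 names no test, and the Table 31 shell has no p-value.

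**Grades.** Protocol 6.0, 9.1 and Appendix I collect grade 2 or higher only. Tables 31 and 32 nevertheless have a grade 1 column and an *Any grade* total, and they stop at grade 4. Table 32 also has a block headed "Patients with fatal AE within category".

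**The concern.** Every patient enters with a painful spinal metastasis (Protocol 5.1.2). The expected effects of radiotherapy listed in Protocol 3.1.1.1 include fatigue, soreness and pain flare, which overlap with symptoms of the disease. A worst-grade table cannot tell a grade 2 symptom that was there at entry and stayed at grade 2 from one that appeared or worsened after treatment. The baseline record was collected in a form that would allow this distinction, but the SAP never links it to the on-study record.

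At stake is the by-arm safety comparison. Persisting symptoms raise the count in both arms, pull the ratio of rates toward 1 and add variance, so an excess on SBRT is easier to miss. If symptoms persist to a different extent in the two arms, the comparison is biased, and the documents do not tell us in which direction.

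**Working it through.** **The plan's own figure.** The documents give no adverse event rate, power or sample size for safety. The only related figure is the primary endpoint's N of 228 (SAP 1.2: 17% vs 34%, two-sided 5%, 80% power). The pooled two-proportion formula gives 103 per arm. With the continuity correction it gives 114 per arm, and 2 × 114 = 228, so that figure reproduces. It has no bearing on this point beyond indicating arm size.

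**Is baseline grade used anywhere?** Baseline events feed Table 8. Tables 31, 32 and 32b contain no baseline grade, and no section defines an event as new or as worse than baseline. Table 8 allows a comparison with baseline at arm level, but not within a patient.

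**Illustration of size.** All inputs here are assumptions:

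- n = 110 treated patients per arm (a little under 114);
- e = new-event rate among patients free of the symptom: 10% CRT, 25% SBRT;
- b = share of patients with the symptom at baseline, which persists without worsening, equal in both arms;
- a = share of those persisting symptoms recorded as radiotherapy-related, equal in both arms.

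Rate shown in Table 31 = a·b + (1 − b)·e. Rate of new events = (1 − b)·e.

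Power = Φ[(d − 1.96·SE0)/SE1], where d is the rate difference, SE0 uses the pooled rate and SE1 the separate rates.

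Worked case, b = 20%:

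- With a = 100% the rates are 0.20 + 0.80 × 0.10 = 28% and 0.20 + 0.80 × 0.25 = 40%. SE0 = √(0.34 × 0.66 × 2/110) = 0.0639 and SE1 = √[(0.28 × 0.72 + 0.40 × 0.60)/110] = 0.0634. Power = Φ[(0.12 − 0.1252)/0.0634] = 47%.
- New events only: 8% and 20%, SE0 = 0.0468, SE1 = 0.0461. Power = Φ[(0.12 − 0.0917)/0.0461] = 73%.

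| Share attributed (a) | b = 20%: rates CRT, SBRT | Power | b = 40%: rates CRT, SBRT | Power |
|---|---|---|---|---|
| 100% | 28%, 40% | 47% | 46%, 55% | 27% |
| 50% | 18%, 30% | 55% | 26%, 35% | 30% |
| 25% | 13%, 25% | 62% | 16%, 25% | 38% |
| 10% | 10%, 22% | 68% | 10%, 19% | 47% |
| New events only | 8%, 20% | 73% | 6%, 15% | 59% |

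With b = 0 both methods give 84%. Within each b the absolute difference is the same in every row (12 points, or 9 points). The loss comes from the added variance, and the ratio falls from 2.5 to 1.43 at b = 20%, a = 100%.

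**If the background is not equal by arm.** Keep b = 20%, but let all persisting symptoms be counted on CRT and half on SBRT. The table then shows 28% vs 0.10 + 0.20 = 30%, a 2-point difference in place of 12. Reversed, it shows 0.10 + 0.08 = 18% vs 40%, a 22-point difference.

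**The case against.** The strongest reply is SAP 2.7.1.1, which restricts Table 31 to events related to radiotherapy. A symptom that merely persists from the cancer is what such a filter is meant to remove. A reader might infer from SAP 2.7.1 that Table 31 counts every symptom after randomization. The documents do not support that, because of this restriction and because only grade 2 or higher events are reported. The filter is incomplete, however. SAP 2.7.1 and the table's title (which takes in intercurrent illness) contradict it, and the shell has no attribution column. The trial is not blinded, and the only definition of relatedness, given for serious events, covers anything for which a relationship cannot reasonably be ruled out.

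A reader might also infer that the background is the same constant in both arms, so that the effect is always dilution. That is an assumption. The trial tests whether SBRT relieves more pain, so persistence of pain may well differ by arm.

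Nor do the power figures describe a test in the SAP. It names none for adverse events, and the tests in Protocol 14.6 concern acute severe events, not worst grade 2 or higher. The figures only illustrate the loss of information.

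Finally, the main safety questions are partly protected. Fracture and cord compression have their own table by treated site (shell 32b), and pain flare is evaluated separately (Protocol 9.1). Such events have little baseline background. All of this narrows the point. What stands is that no rule uses the patient's own baseline grade.

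**Conclusion.** The point holds in a limited form. Table 31 ignores baseline grades that were collected to document symptoms present before treatment, so some of those symptoms can be counted as on-study events. The SAP also disagrees with itself on whether the table is radiotherapy-related or all-cause, and with the protocol on when counting starts.

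The size cannot be computed from the documents: prevalence, persistence, attribution and new-event rates are all missing. Under the stated assumptions at 20% prevalence, power runs from 47% (all persisting symptoms attributed) to 68% (a tenth attributed), against 73% for new events. The low end is the worst case for that prevalence. At 40% prevalence the range is 27% to 47%, against 59%. These ranges need balance between arms; without it the bias could go either way. Terms with little baseline background are hardly affected. The grade-column errors are certain but minor, since deaths also appear in Tables 23 and 34.

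**What to change.** 1. Base the by-arm comparison on events that are new, or of higher grade than the patient's own baseline grade for the same CTCAE term. Treat an unreported baseline as grade 0–1. Keep the all-events worst-grade table as supplementary.
2. Count from first treatment, as in Protocol 10.1.4, and align SAP 2.7.1 with it. Appendix I schedules no adverse event evaluation on Day 0, so a symptom that starts between randomization and the first fraction and then persists would still look new. Use onset dates to exclude it if they are recorded (the documents do not say); otherwise add a footnote.
3. Reconcile SAP 2.7.1, 2.7.1.1 and the Table 31 title on radiotherapy-related versus all-cause events. If both are wanted, show both.
4. State in SAP 2.7 whether the Protocol 14.6 tests apply, and to which event definition.
5. In Tables 31 and 32, drop the unused grade 1 column, relabel *Any grade* as grade 2 or higher, and add a grade 5 column.

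Cost: SAP wording, one merge by patient and CTCAE term, and one extra table. The planned collection already supplies the baseline and on-study grades. The downside is a slightly smaller group at risk for each term.
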